# 3.1.1.3 Epidemiology of HPV Infection and Disease

### 3.1.1.3.1 HPV Infection

The cumulative lifetime risk for HPV infection in sexually active women exceeds 50%. Available data suggest that HPV infection is also very prevalent in men [34; 35]. HPV infection is transmitted via contact with an infected individual or a contaminated object and occurs most often during sexual activity. Sixty percent (60%) of sexual partners of infected individuals develop lesions 4 weeks to 8 months after exposure [36]. HPV is often acquired immediately after sexual debut. The risk of HPV infection is strongly correlated with the number of lifetime sexual partners [37; 38]. Men and women in their late teens and early twenties are at the highest risk for HPV infection, as early sexual activity is accompanied with a higher likelihood of having new sexual partners, thus increasing the risk of exposure to the virus. The incidence of HPV infection in women increases with age during the teen years and peaks in the early 20's and declines gradually thereafter [6; 39]. In contrast, there does not appear to be such an association between HPV prevalence and age in men. This difference between genders may reflect stronger immune response to HPV in women, as suggested by findings of higher prevalence of anti-HPV antibodies in women than in men across all ages [40]. Most cervical HPV infections resolve spontaneously. On average, HPV infection persists for 4 to 20 months. However, a small proportion of infections persist beyond 1 to 2 years. Infection with HR types tends to last longer than infection with low-risk (LR) types [41; 42: 43: 44: 45].

23

### 3.1.1.3.2 Cervical HPV Disease

[figure not shown]
Infection with HPV is generally asymptomatic and not recognized until lesions are identified. Most HPV lesions are self-limited: for instance, early HPV disease causes low-grade cervical dysplasia (Cervical Intraepithelial Neoplasia Grade 1 [CIN 1]) which resolves in most cases without clinical sequelae. In some cases however, HPV infection persists, leading to CIN 2/3 and cervical cancer [39]. CIN 2/3 encompasses moderate and high-grade cervical dysplasia and cervical carcinoma in situ. It is the immediate precursor to cervical cancer with high rates of progression to cervical cancer and low rates of regression to normal [46]. Determinants of progression versus clearance of HPV disease are not well defined. Pap test screening programs have sharply reduced cervical cancer incidence [47] by allowing early detection and excision of CIN 2/3 lesions prior to cancer development [48; 49]. These benefits have not been shared in populations with sporadic screening, especially in the developing world and among the disadvantaged in the US [50].

It appears that viral persistence, rather than transient viral infection, plays a key role in cervical carcinogenesis [51; 52; 53; 54; 55]. Risk of CIN and invasive cervical cancer (ICC) is strongly associated with persistent infection with HR types [56; 57; 39; 58; 59; 60]. Persistent detection of HR HPV DNA is a predictor for progression to cervical cancer [39; 61; 62]. The risk of development of cervical lesions, which is highest for HPV 16, has also been demonstrated for other HR HPV types. The risk of progression to CIN increases with duration of viral persistence. However, a long period of infection

(e.g., > 1 year) is often not required for CIN development [63]. A strong association between 3 to 6 months persistent infection and subsequent development of CIN1 or worse has been demonstrated [64]. Based on all these observations, persistent infection with at least 1 HR type is considered a key intermediate step for progression to cervical cancer.

24

The natural history of cervical HPV disease is represented schematically in Figure 3-1.

#### Figure 3-1

Natural History of Infection with High-Risk HPV Types (e.g., HPV 16 and HPV 18)

### 3.1.1.3.3 Non-Cervical HPV Disease

Infection with HPV is also associated with vulvar, vaginal, anal, penile, oral, and oropharyngeal cancers [2; 3]. Each of these HPV-related diseases is much less frequent than cervical cancer. But taken together, they represent a significant human health and economic burden [34; 65]. Of particular concern, the incidence of anal cancer has been increasing over the past several decades [66]. The risk of anal cancer is increased in men and women with a high number of sexual partners, current smokers, and among men who are not exclusively heterosexual or women by having sexual intercourse [67]. Anal cancer is preceded by high-grade anal intraepithelial neoplasia (AIN) [68; 69]. Over 80% of anal cancers and over 90% of high-grade anal neoplasia contain HR-HPV [70]. The high proportion of HPV-positive tumors suggests that HPV infection is necessary for developing anal cancer. HPV vaccination could prevent most anal cancers and precancers.

# 3.1.1.3.4 Aspects of HPV Infection and Disease Specific to Men

Only a few prospective studies have examined the incidence and duration of genital HPV infection in men. These studies indicate that HPV infection in men is self limited and a risk factor for HPV genital disease. Most HPV infections in men appear to clear within 12 months with a median time of clearance ranging from 5.9 to 7.5 months [71; 72]. HPV 16 infections tend to last longer and clear at an average of 12.2 months [72]. HPV testing positive for HPV 6 or 11 is the strongest predictor of developing genital warts [73]. HPV 16 infection is a recognized risk factor for penile cancer [74].

25

# **3.1.1.4 Prophylactic HPV Vaccines**

### 3.1.1.4.1 Immune Response to HPV Natural Infection and HPV Vaccination

By remaining exclusively intraepithelial, HPV largely avoids exposure to the host immune system and evades immune recognition, which allows HPV infection to proceed [10; 75; 76]. Other mechanisms inhibiting the immune response are also used by HPV to avoid immune surveillance and control [77]. Accordingly, immune responses to natural viral infection are poor. In particular, low-level antibody responses to HPV become detectable only several months after the infection and in only approximately 50% of the subjects [78]. Nonetheless, most HPV infections are eventually cleared. It is thought that naturally acquired immune responses contribute to the clearance of infection, although the mechanisms are not well elucidated [79]. Those infections that are not cleared (especially the high-risk types) can result in dysplasia and cancer.

Prophylactic HPV vaccines have been developed based on VLPs which are produced by self-assembly of recombinant HPV L1 capsid proteins expressed in a heterologous cell substrate. VLPs mimic the overall structure of HPV virions, thus keeping capsid proteins in their native antigenic conformation. HPV vaccines are delivered intramuscularly and induce high levels of type-restricted neutralizing antibodies to L1 and seroconversion in virtually 100% of the vaccinated subjects.

### 3.1.1.4.2 Quadrivalent HPV (qHPV) Vaccine

### 3.1.1.4.2.1 Phase III Clinical Studies

As of July 2012, the quadrivalent (Type 6, 11, 16, 18) HPV L1 VLP vaccine (qHPV vaccine) was approved and marketed under the name GARDASILTM/SILGARDTM in over 120 countries. A 0.5-mL dose of vaccine contains 20 µg HPV Type 6 L1 VLP, 40 µg HPV Type 11 L1 VLP, 40 µg HPV Type 16 L1 VLP, 20 µg HPV Type 18 L1 VLP, and 225 µg of the adjuvant Amorphous Aluminum Hydroxyphosphate Sulfate (AAHS).

In clinical trials in 16 to 26-year-old women, qHPV vaccine was over 94% efficacious in preventing the development of: HPV 16- and 18-related CIN 2/3 and adenocarcinoma in situ (obligate cervical cancer precursors); HPV 16- and 18-related Vulvar Intraepithelial Neoplasia (VIN) 2/3 and Vaginal Intraepithelial Neoplasia (VaIN) 2/3 (obligate precursors to HPV-related vulvar and vaginal cancer, respectively); HPV 6- and 11- related external genital lesions (including condyloma acuminata); HPV 6-, 11-, 16-, and

18-related CIN; and HPV 6-, 11-, 16-, and 18-related persistent infection [80]. Efficacy was maintained for at least 5 years post-vaccination onset [81]. The vaccine also afforded some cross-protection against other oncogenic HPV types [82; 83; 84]. However, cross-protection was incomplete and limited to only a few types. In addition, in a Phase III study (V501 Protocol 020), the qHPV vaccine was over 89% efficacious in preventing the development of HPV 6- or 11-related genital warts in 16- to 26-year-old males [85], and 77.5% efficacious in preventing AIN in 16- to 26-year-old men-having-sex-with-men (MSM) [86].

26

#### 3.1.1.4.2.2 Ecological Studies

Australia has been the first country to introduce a fully funded national HPV vaccination program. The program, targeted to adolescent females 12 to 13 years of age, was started in April 2007. In addition, up to 31-Dec-2009, a catch-up vaccination program was offered to girls and women, 14 to 26 years of age [87]. Within approximately 3 years following implementation of this qHPV vaccination program, a decline was observed in the diagnosis of genital warts among young Australian women [88]. Moreover, a decrease was noted in incidence of high-grade cervical abnormalities in girls less than 18 years of age [89]. A subsequent study reported the near disappearance of genital warts in young women and young heterosexual men within approximately 4 years following implementation of this vaccination program [90]. Overall, these observations suggest a rapid, beneficial effect of mass vaccination with qHPV vaccine. Dramatic fall in disease incidence following vaccine introduction, a typical pattern previously observed after introduction of mass vaccination with a number of new vaccines, appears also verified with qHPV vaccine. The decline in genital warts among Australian men (who are not part of the mass vaccination program) indicates that the concept of herd protection, previously noted with other vaccines, is also applicable to prophylactic HPV vaccination.

### 3.1.1.4.3 V503: 9-valent Prophylactic HPV Vaccine

The 9-valent HPV L1 VLP vaccine formulated with AAHS consists of highly purified VLPs of the L1 capsid proteins from HPV 6, 11, 16, 18, 31, 33, 45, 52, and 58. Like for GARDASILTM, the L1 capsid proteins in the vaccine are individually expressed in *Saccharomyces cerevisiae* yeast. The HPV 6, 11, 16, 18, 31, 33, 45, 52, and 58 L1 VLPs final aqueous products consist of recombinant L1 polypeptides for their respective viral types that have self-assembled into VLPs. Following fermentation, the VLPs are isolated from lysed yeast cells by standard techniques, then highly purified, and then adsorbed onto AAHS without the addition of preservative. After preparation of the Monovalent Bulk Adsorbed Products, the bulks are mixed to create the 9-valent HPV L1 VLP vaccine with the desired concentrations of each monovalent L1 VLP. The 9-valent HPV L1 VLP vaccine is not a live virus vaccine. It is not capable of causing viral infection.

HPV 16 and 18 cause approximately 70% of cervical cancers worldwide. Approximately 20% of additional cervical cancers are caused by HPV 31, 33, 45, 52, and 58. The addition of HPV 31, 33, 45, 52, and 58 L1 VLPs to the 4 types already present in qHPV vaccine will thus increase overall cervical cancer coverage from approximately 70% to approximately 90% [91; 92]. Assuming at least 90% vaccine efficacy, this coverage may

provide 80% or greater reduction in cervical cancer risk (matching or exceeding the efficacy of most cervical cancer screening programs). A small increase in coverage of anal, vulvar, and vaginal cancers and precancers is also anticipated.

27

#### 3.1.2 Rationale for This Study

#### 3.1.2.1 Rationale for Assessment of Long Term Effectiveness

Protocol V503-002, a 12-month immunogenicity and safety study of V503 in preadolescent and adolescent girls and boys, showed that V503 is highly immunogenic and generally well-tolerated in the study population. Girls and boys enrolled in V503-002 are being followed for 24 additional months under Study Extension V503-002-10, to assess persistence of antibody responses and long term safety.

Taken together, the Protocol V503-002 base study and V503-002-10 study extension will provide immunogenicity and safety data through approximately 36 months of study follow-up. Efficacy data were not collected in V503-002 and V503-002-10 because evaluation of sexual history and gynecological/genital examination is limited in young adolescents by social, cultural, and legal constraints. Nonetheless, data on the long term immunogenicity, safety, and effectiveness of V503 administered to preadolescent and adolescent girls and boys will support ongoing use of the vaccine in this important target population.

In the current protocol, immunogenicity and safety information will be collected for all subjects, and effectiveness endpoints will be assessed in subjects who have reached 16 years of age. Collection of efficacy data will be dependent on age and gender. Data permitting, the protocol will evaluate the long term effectiveness of V503 in preventing HPV persistent infection as well as HPV disease caused by HPV types targeted by V503, including external genital warts in both genders; cervical, vulvar, and vaginal intraepithelial neoplasia, and associated cancers in female subjects; penile, perineal, and perianal intraepithelial neoplasia, and associated cancers in male subjects.

#### **3.1.2.2 Rationale for Including Male Subjects**

HPV vaccination could contribute to reducing the burden of HPV diseases in males. The qHPV vaccine is highly efficacious to prevent genital warts as well as anal cancer and precancers in males. Additional benefits of vaccination may include coverage of other HPV-related cancers (i.e., head and neck cancer, penile cancer) for which prophylactic vaccine efficacy has not been studied but is biologically plausible. In contrast to cervical cancer in women, there is no widespread screening program for any of the HPV-related cancers in men. Thus, prophylactic vaccination is the only realistic preventive measure for HPV diseases in men, in both developed and developing countries.

A number of observations suggest that HPV transmission is a risk for development of HPV disease in both men and women. Male factors, such as lack of circumcision (which promotes chronic HPV infection in men), type-specific HPV infection, and viral load of such infection, are important correlates for HPV infection and disease in their female partners [93; 94; 95; 96]. Penile lesions are frequent in sexual partners of women with

CIN [97; 98]. Regression of penile lesions is significantly slower in men whose partners are infected with the same HPV type [99]. Husbands of women with cervical cancer or cervical carcinoma in situ have a higher HPV prevalence than husbands of control women [100]. The risk of cervical cancer is also increased by certain behaviors of male partners, such as having multiple sex partners and contact with prostitutes [101; 102]. Thus, vaccination of men could promote herd protection and lead to a substantial reduction of HPV-related diseases in both males and females [35].

Previous public health experience has shown that gender-restricted vaccination programs are substantially less effective than universal vaccination. It is likely that the most effective means to reduce the burden of HPV disease through vaccination is to vaccinate both males and females. As illustrated by the Australian experience, the concept of herd protection is applicable to HPV prophylactic vaccination. Thus, in the setting of a protective intervention that provides less than 100% protection to the entire female population (i.e., less than 100% efficacy and/or less than 100% coverage), reducing the burden of HPV disease would likely be enhanced by gender neutral vaccination through the establishment of herd protection.

#### **3.2 STUDY PROCEDURES**

# **3.2.1** Prerequisites for Study Visits With Gynecological or Genitourinary Specimen Collection

All subjects 16 years of age and older will have gynecological (female subjects) or genitourinary (male subjects) specimens collected during study visits. This section summarizes prerequisites for visits with collection of such specimens. Deviations from these prerequisites require consultation between the investigator and the SPONSOR and written documentation of the collaborative decision. See the Administrative Binder for a summary of deviations that require documentation in this study

For visits that include collection of study specimens, study personnel should verify by questioning the subject and/or by examination that:

- (All subjects) The subject has refrained from sexual activity (including anal, oral, vaginal, or genital/genital contact, whether same sex or opposite sex) for 2 calendar days prior to any visit that includes collection of labial/vulvar/perineal and perianal (LVPP) swabs, endo/ectocervical (EEC) swabs or external genital swabs, a Pap test, and/or biopsies/definitive therapy specimens.
- 2. *(Female subjects only)* The subject has refrained from douching/vaginal cleansing and using vaginal medications or preparations for 2 calendar days prior to any visit that includes collection of LVPP/EEC swabs, a Pap test, and/or biopsies/definitive therapy specimens.
- 3. *(Female subjects only)* The subject does not have visible blood in the vagina. As a guide, a study visit that includes collection of LVPP/EEC swabs, a Pap test, and/or biopsies/definitive therapy specimens should not be scheduled between the time

period of 2 days prior to menses (if date of menses can be predicted) to 2 days after menses. If, despite using these collection timeframe guidelines, visible blood is noted in the vagina, then the specimens may be collected.

29

- 4. *(Female subjects only)* The subject does not have gross purulent cervicitis at a study visit that includes collection of LVPP/EEC swabs, a Pap test, and/or cervical biopsies/definitive therapy specimens.
- 5. *(Male subjects only)* The subject has refrained from shaving his genital region (and/or applying any post-shave solutions or lubricants) a minimum of 1 day prior to the visit as this may interfere with the collection of skin cells. If the subject has shaved, or applied lotions or lubricants within 24 hours, the scheduled visit, exam, and specimen collection will be postponed until this criterion has been met.

If the subject does not meet the requirements listed above, the study visit (including specimen collection and/or study vaccination) should be re-scheduled. If the subject has gross purulent cervicitis, the re-scheduled study visit should occur after the condition is diagnosed and treated according to the study site's standards and practices.

# 3.2.2 Summary of Scheduled Study Visit Procedures

The Study Flow Chart summarizes procedures for scheduled study visits and items appear in the order they should be performed. This section provides clarifications to the scheduled study visit procedures (presented in order of the Study Flow Chart).

# **3.2.2.1 Calculation of Schedule Visit Windows**

The visit windows provided in this protocol are for site scheduling purposes. The visit windows used for exclusion from analyses are provided in the Statistical Analysis Plan (Section 3.5). The Day 1 visit was defined as the day that the first study vaccination was given during the V503-002 Base Study. The Month 6 visit (when the third vaccination was given during the Base Study) was based on Day 1 and had a  $\pm 4$  weeks visit window. The Month 36 visit in Extension 002-10 was based on Month 6 and had  $\pm 4$  weeks visit window. The Month 42 visit in Extension 002-20 is based on Month 36 and has  $\pm 4$  weeks visit window. The other study visits in Extension 002-20 are each based on Month 42 and have a  $\pm 4$  weeks visit window. To calculate visit windows, assume 1 month equals 30 days and 1 week equals 7 days.

### **3.2.2.2 Informed Consent**

Written consent will be obtained for each subject (or, for minors, from the parent/legal guardian and the subject) prior to enrollment, study data collection, or performance of study procedures. A copy of the signed informed consent form will be given to each subject for his or her records. Verification of the subject's identity and age is to be determined prior to obtaining written consent. Any government-issued photo identification will suffice for verification purposes and should be documented in the subject's file.

The assent/consent for the V503-002-20 Extension can be collected at the Month 36 visit (if possible), or can be administered prior to serum collection at the Month 42 visit.

30

#### **3.2.2.3 Randomization/Allocation**

Subjects were randomized in the Protocol V503-002 Base Study and will retain their baseline and allocation numbers from those studies.

A single patient/subject cannot be assigned more than 1 allocation number.

### 3.2.2.4 Patient ID Card

All subjects/patients will be given a card, at the time of screening, identifying them as participants in a research study. The card will contain contact information (including direct telephone numbers) to be utilized in the event of an emergency.

#### **3.2.2.5 History and Medication**

No study vaccinations will be administered during the follow-up period. If an investigator discovers that a subject received an additional dose of any marketed HPV vaccine unintentionally outside the context of the study, this should be reported to the Sponsor.

Limited new medical history information will be collected to include:

- Events of acquired immunodeficiency
  - $\circ$  HIV infection
  - Hematological malignancies (e.g., leukemia, lymphoma) 0
  - Immunosuppressive therapy or procedure such as radiation therapy, 0 cytotoxic or immunosuppressive chemotherapy, high-dose corticosteroids (at least 2 weeks), immunosuppressive monoclonal antibody therapy (e.g., anti-CD20, anti-TNF-alpha), splenectomy, or any other therapy or procedure known to interfere with the immune response.
- Administration of a marketed HPV vaccine outside the context of the study.
- Any gynecological or genitourinary procedure or condition that may interfere • with the evaluation of vaccine effectiveness (e.g., subject had hysterectomy, subject has more than 1 cervix uteri).
- Any condition that may be relevant to the evaluation of the vaccine.

#### **3.2.2.6 Sexual History and Contraception Information**

At the first visit after a subject reaches 16 years of age, the subject's lifetime sexual history will be collected. For subjects who are sexually active, additional information will be collected to determine the age at sexual debut, the date of last sexual event, the

lifetime number of sex partners, the number of new or current sexual partners, and use of contraception. In this context, sexual activity is defined as having had vaginal and/or anal penetration and/or oral sex and/or genital to genital contact.

31

If a subject <16 years of age volunteers information relating to their sexual debut, then information similar to that described above will be gathered.

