# 2.7.2 Effectiveness

At the time of the first interim analysis (Month 72), summaries of the incidence of HPV 6, 11, 16, 18, 31, 33, 45, 52, and 58 related persistent infection for a duration of  $\geq 6$  months (within  $\pm 1$  month windows) and cervical, vulvar, vaginal, perineal, perinal, and penile intraepithelial preinvasive and invasive disease, and external genital lesions will be provided, separately for males and females. Similar summaries of the incidence rates of HPV 6, 11, 16, 18, 31, 33, 45, 52, and 58-related persistent infection for a duration of  $\geq 6$  months (within  $\pm 1$  month windows) and disease will be provided to include follow-up data through the second interim analysis at Month 96 and at the end of the study at Month 126.

All subjects will contribute to the effectiveness summaries. Summaries will be provided by gender and age group (based on age at enrollment). The primary analysis group will be those who have received 3 doses of 9-valent HPV L1 VLP vaccine within one year. Subjects will be considered breakthrough cases related to a given HPV type provided they were negative to the respective HPV type by serology prior to vaccination and were sexually naïve through the 3rd dose of 9-valent HPV L1 VLP vaccine. Sexual naïveté, an inclusion criterion for the base study, is being used as a way to limit analysis of the prophylactic effect of the vaccine to subjects who were not infected prior to completion of the vaccination series. There are no PCR data from Protocol V503-002 subjects until subjects reach their 16th birthday. Therefore, the only data available to assess possible prior infection are pre-vaccination serum anti-HPV levels and sexual history. Cases in subjects with evidence of HPV exposure or infection prior to vaccination (i.e., seropositivity to the relevant HPV type(s) pre-vaccination or sexual activity prior to completion of the vaccination series) or in subjects who did not receive 3 doses of 9valent HPV L1 VLP vaccine within one year will not be considered breakthrough cases (vaccine failures). Such cases will be summarized separately.

20

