### **3.2.2.10** Gynecological or Genitourinary Examination and Sample Collection

There will be no gynecological or genitourinary examination and sample collection in subjects who are less than 16 years of age.

Once a subject becomes 16 years of age, gynecological or genitourinary examination and sample collection will be performed at every study visit. Gynecological examination and sample collection in female subjects will be different in subjects 16 to 20 years of age who are not sexually active, subjects 16 to 20 years of age who are sexually active, and subjects  $\geq 21$  years of age. In this context, 'sexually active' is defined as having had vaginal penetration. Genitourinary examination and sample collection will be conducted in all male subjects 16 years or older regardless of sexual history.

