#### Per-Protocol Effectiveness (PPE)

The PPE analysis population is HPV type-specific. In analyses of endpoints related to a specific HPV type (e.g., HPV 16-related endpoints) the PPE population-eligible subjects include those who:

- (1) received 3 doses of 9-valent HPV L1 VLP vaccine within 1 year; AND
- (2) were seronegative by cLIA to the specific HPV type at the time of injection of dose 1 of 9-valent HPV L1 VLP vaccine (seronegative to both types 6 and 11 in analysis of HPV 6-related, and HPV 11-related endpoints); AND
- (3) Have no other protocol violations that could interfere with the evaluation of the effectiveness of the study vaccine. Specifically, at base study Day 1, satisfied inclusion criterion 5 (i.e., " Subject must not yet have had coitarche and does not plan on becoming sexually active during the Day 1 through Month 7 period.") specified in Section 2.2 of the protocol of the base study (i.e., Protocol V503-002-00).

Inclusion criterion 5, at base study, was intended to capture subjects who had not yet been infected with HPV through sexual intercourse and were therefore likely to be HPV-naïve during the period of vaccination with 9-valent HPV L1 VLP vaccine. The seronegativity condition is another criterion intended to capture subjects who were still HPV-naïve during the period of vaccination of 9-valent HPV L1 VLP vaccine

Note that a subject can be both PPE population-eligible for analyses of endpoints related to one HPV type (e.g., HPV 16-related endpoints) and PPE population-ineligible for analyses of endpoints related to another HPV type (e.g., HPV 18-related endpoints).

In analyses of endpoints related to any vaccine HPV type (e.g., HPV 6/11/16/18/31/33/45/52/58-related endpoints), the PPE population-eligible subjects include those who are PPE population-eligible for *any of* the HPV types 6, 11, 16, 18, 31, 33, 45, 52, or 58.

Only PPE population-eligible subjects who are at least 16 years of age and have at least one follow-up visit with PCR data will contribute to the PPE analyses.

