#### **3.5.5.3 Statistical Methods for Effectiveness Analyses**

Subjects who meet the criteria to be considered cases of vaccine type HPV-related persistent infection and/or disease, but who have evidence of HPV exposure or infection (i.e., seropositivity to the respective HPV type(s) pre-vaccination or evidence of sexual activity prior to the completion of their vaccination series), or who do not complete their three doses of 9-valent HPV L1 VLP vaccine within one year, will not be considered breakthrough cases (i.e., vaccine failures). Such cases will be summarized separately in a manner similar to breakthrough cases, with all relevant factors such as baseline demographics and immunogenicity profiles over time characterized; however, these cases will not be included in the primary summary of effectiveness endpoints.

78

At the time of the interim analysis (Month 72), summaries of the incidence of HPV 6, 11, 16, 18-related persistent infection for a duration of  $\geq 6$  months (within  $\pm 1$  month windows) and cervical, vulvar, vaginal, perineal, perinanal, and penile intraepithelial preinvasive and invasive disease, and external genital lesions will be provided, separately for males and females. Similar summaries of the incidence rates of HPV 6, 11, 16, 18, 31, 33, 45, 52, and 58-related persistent infection for a duration of  $\geq 6$  months (within  $\pm 1$  month windows) and disease will be provided to include follow-up data through Month 96 and Month 126.

The confidence intervals around the point estimate of the incidence rates per 100 personyears are exact Poisson distribution-based nominal 95% confidence intervals.

Summaries will be provided by gender. At each analysis time point, the cumulative incidence rate for effectiveness endpoints will be computed, along with the associated 95% confidence interval. In addition, exploratory analyses will be conducted to characterize subjects who become cases of persistent infection or disease endpoints in the long-term effectiveness follow-up period. Baseline demographic characteristics, prevaccination anti-HPV serology status, and post-vaccination immunogenicity profiles will be considered. Time-to-event plots will also be provided by gender if >5 cases are observed in the respective group(s).

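### Cases in per-protocol subjects can leave the primary effectiveness summary for undefined sexual activity before dose 3, while their person-time stays in the denominator

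*Combined protocol and SAP*

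**What the plan says.** Four parts of the combined protocol and SAP bear on this.

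- **Who enters the primary population.** Section 3.5.4.3 makes the PPE primary. Its third condition excludes protocol violations that could interfere with the evaluation, and then narrows this: "Specifically, at base study Day 1, satisfied inclusion criterion 5". That criterion reads "Subject must not yet have had coitarche and does not plan on becoming sexually active during the Day 1 through Month 7 period".
- **Which cases count.** Section 3.5.5.3 denies breakthrough status to a case where there is "evidence of sexual activity prior to the completion of their vaccination series". Of the cases removed on this and related grounds it says "these cases will not be included in the primary summary of effectiveness endpoints". Section 2.7.2 gives the same rule as sexual naïveté up to the third dose and describes that naïveté as a base-study inclusion criterion. Neither section defines sexual activity.
- **What data are used.** Section 2.7.2 states that "the only data available to assess possible prior infection are pre-vaccination serum anti-HPV levels and sexual history". Under Section 3.2.2.6, at the first visit from age 16, "the subject's lifetime sexual history will be collected", and the definition given there is "In this context, sexual activity is defined as having had vaginal and/or anal penetration and/or oral sex and/or genital to genital contact".
- **A further definition for sampling.** Section 3.2.2.10 says: "In this context, 'sexually active' is defined as having had vaginal penetration".

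Section 3.5.5.3 reports rates per 100 person-years with exact Poisson intervals. Section 3.5 says no separate SAP will be issued, so this text has to settle the matter.

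**The concern.** The rule that admits subjects and the rule that removes cases differ in two ways.

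- **Definition.** Admission turns on coitarche and stated intent. Removal turns on an undefined term, judged from a history that also counts oral sex and genital-to-genital contact.
- **Time.** Admission is judged at Day 1. Removal looks at the whole period up to completion of the series.

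A subject who falls between the two rules stays in the PPE and contributes follow-up time, but cannot contribute a breakthrough case. The incidence rate then loses events from the numerator with no matching loss from the denominator. The extension has no unvaccinated comparator, so the absolute rate is the result that readers will use, and an understated rate favours the vaccine.

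**Working it through.** The plan gives no figure to reproduce: the sample size is fixed, there is no hypothesis, and no expected case count or exposure prevalence is stated. The check is first a comparison of the rules, then an illustration of direction and scale.

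**Step 1. The rules side by side**

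| | PPE eligibility (3.5.4.3) | Breakthrough rule (2.7.2, 3.5.5.3) | Sexual history (3.2.2.6) |
|---|---|---|---|
| Exposure | Coitarche, or a plan to become sexually active | Sexual activity, undefined | Penetration, oral sex or genital-to-genital contact |
| Time | Base study Day 1 | Up to completion of the series | Lifetime |
| Consequence | Subject in or out | Case in or out | None stated |

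**Step 2. Two subjects**

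- A girl enrolled at 15 has had oral contact but no coitarche, has no plan to become sexually active, is seronegative for HPV 16 and receives three doses within a year. She meets the PPE conditions. If she later becomes an HPV 16 case, her lifetime history shows sexual activity before dose 3 under the Section 3.2.2.6 definition, so her case can be removed.
- A boy meets criterion 5 at Day 1 but has unplanned intercourse before dose 3. Criterion 5 as judged at Day 1 still holds, yet his later case is removed under any of the definitions. This gap comes from timing, so aligning the definition alone would not close it.

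Neither Section 3.5.4.3 nor Section 3.5.5.3 says that either subject's person-time is removed.

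**Step 3. Direction and scale (all inputs assumed)**

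Let f be the share of PPE person-time from affected subjects, and k their case rate relative to the other subjects. With the other subjects' rate set to 1:

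- all cases and all person-time kept: (1 − f) + f·k
- cases removed, person-time kept: 1 − f
- cases and person-time both removed: 1

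The ratio to the keep-all rate is A = (1 − f)/[(1 − f) + f·k]. The ratio to the remove-both rate is B = 1 − f.

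| f | k | A | B |
|---|---|---|---|
| 2% | 1 | 0.98/0.98 + 0.02 in the denominator = 0.98/1.00 = 0.98 | 0.98 |
| 5% | 2 | 0.95/(0.95 + 0.10) = 0.905 | 0.95 |
| 10% | 3 | 0.90/(0.90 + 0.30) = 0.75 | 0.90 |
| 20% | 3 | 0.80/(0.80 + 0.60) = 0.571 | 0.80 |

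Both ratios are below 1 whenever f and k are above zero. Against either coherent alternative the bias is downward.

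**Step 4. Illustration with counts**

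Assume 20 cases in 5000 person-years, f = 10% and k = 1, so that 2 cases and 500 person-years belong to affected subjects.

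- Keep all: 20/5000 = 0.40 per 100 person-years (exact 95% CI 0.24 to 0.62).
- Remove cases only: 18/5000 = 0.36 (0.21 to 0.57).
- Remove both: 18/4500 = 0.40 (0.24 to 0.63).

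The shift is small against the width of the interval, but it is systematic and more data would not reduce it.

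**The case against.** **What can be said for the plan.** A broad exposure screen fits the aim in Section 2.7.2 of limiting the analysis to subjects not infected before completing vaccination. Removed cases are summarised separately in a similar way, and the full analysis set carries no sexual-history condition. The study is for estimation only. The general clause on protocol violations in the PPE definition might also be used to exclude such subjects. These points soften the problem but leave the primary summary uncorrected. If a broad screen is intended, it should govern eligibility and person-time as well as cases. The full analysis set also admits baseline seropositive subjects, so it does not isolate this effect. The general clause, as written, specifies only criterion 5 at Day 1.

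**Stronger readings that the documents do not support.**

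- A reader might infer that Section 3.5.5.3 orders removal for oral or genital contact. It does not. The Section 3.2.2.6 definition is limited to its own context, and neither analysis section cites it. Removal on that basis is permitted by an undefined term.
- A reader might infer that the mismatch cannot be undone at analysis. The case-report form is not shown, and age at debut is only one of several items collected. Girls aged 16 to 20 are also classified by vaginal penetration, with sexual history updated at each visit. A girl enrolled before her 16th birthday is under 19.5 at Month 42 (16 + 3.5), so every girl followed from then passes through that classification. A gap may remain for boys, and for girls who had already had intercourse at their first visit from age 16.
- A reader might infer that a missing cervical swab at 16 to 20 cannot be interpreted. The flow chart strata, set by vaginal penetration, show whether a swab was due.

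**Conclusion.** The point holds as an inconsistency between two stated rules. Subjects enter the PPE on a Day 1 criterion, while their cases can be dropped for undefined sexual activity up to dose 3. No provision drops their person-time. The resulting bias in the primary rate per 100 person-years can only be downward.

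Its size cannot be found from the documents. Over an assumed f of 2% to 20%, the primary rate is 0.98 to 0.80 times the remove-both rate. Against the keep-all rate it runs from 0.98 (f = 2%, k = 1) to 0.57 (f = 20%, k = 3); the last figure pairs the most extreme assumed values and should not be read as an expectation. The conclusion rests on reading the silence about person-time as meaning that it is kept. It affects a secondary objective in a study without hypothesis tests, but it touches that objective's primary summary and is cheap to prevent.

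**What to change.** 1. In Sections 2.7.2, 3.5.4.3 and 3.5.5.3, state one definition of prior sexual exposure and one window, through dose 3. Apply it to all subjects whether or not they become cases. Anyone who meets it leaves the PPE with both cases and person-time.
2. Report the alternative definition, wider or narrower, as a sensitivity analysis.
3. Where the case-report form does not already do so, record age at first penetration separately from age at first oral or genital-to-genital contact.

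Simply carrying the Day 1 coitarche condition into the breakthrough rule would not be enough. Infections after intercourse between Day 1 and dose 3 would then count as vaccine failures, contrary to the aim in Section 2.7.2.

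The cost is a wording change in three sections before the Month 72 analysis, some loss of PPE person-time, and at most one added item. Subjects already interviewed would need that item asked at a later sexual-history update, with some reliance on recall.
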